9.2 Complete Response with Incomplete Hematologic Recovery (CRi)

A CR with incomplete hematologic recovery (CRi) is defined as no morphologic, immunohistochemical, or flow cytometric evidence of disease by BM biopsy/aspirate, but with a persistent platelet count $<100,000/\mu\text{L}$ and/or ANC $<1000/\mu\text{L}$ at the time of BM biopsy/aspirate.

9.3 Partial Response (PR)

A PR is an incomplete response to treatment, defined as having persistent disease by morphology, but a $>50\%$ reduction in the blast count/cellularity ratio compared to the most recent BM biopsy prior to treatment.

9.4 Treatment Failure

Treatment failure is defined as patients who have achieved less than a PR at the time of response assessment.

9.5 Duration of Response (DOR)

Duration of response is defined as the number of days from the time of the first BM biopsy/aspirate where CR or CRi is identified to relapse. Patients who demonstrate no evidence of disease and no relapse while on study or who died for reasons other than disease relapse will be censored at the date of the last disease assessment..

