All grades of gastrointestinal toxicities associated with CPX-351 were similar to standard induction 7+3, with the most frequent being nausea (47%), diarrhea/colitis (45%), mucositis (44%), and constipation (40%). However, Grade 3 and higher gastrointestinal toxicities were less than 10% (Lancet et al 2016b). In Phase I/II investigations, quizartinib was found to be associated with all grades of nausea (16%), vomiting (11%), and diarrhea (18%) (Cortes et al 2013, Schiller et al 2014).

Given that the toxicities identified with each agent have minimal overlap, it is hoped that the novel combination will not result in the potentiation of the toxicity of either agent alone. A potential beneficial effect of this combination may be the protective effect of quizartinib on normal hematopoietic progenitor cells after exposure to chemotherapy. If dosed sequentially following CPX-351, this may attenuate the effects that CPX-351 has on healthy stem cells without compromising the effect on the leukemic cells (Taylor et al 2017). This potential benefit of the novel combination will be measured based on the timing of myeloid count recovery and comparing this data to data from prior CPX-351 studies.

It is assumed that there are four patient groups who may derive benefit on study for relapsed or refractory FLT3 mutation-positive AML. The first group includes patients who have primary refractory FLT3 mutation-positive AML and who fail first-line therapy with routine induction regimens with or without an FLT3 inhibitor. The second group includes patients with FLT3 mutation-positive AML who have relapsed after HCT. In both scenarios, the study intervention will likely act as a bridge to either an HCT or a DLI. The third group includes patients with relapsed FLT3 mutation-positive AML who were excluded from or declined alloHCT. In this patient population, the FLT3 inhibitor would continue as maintenance therapy. The final group of patients includes those who acquire an FLT3 mutation at relapse. This occurs more frequently in patients with epigenetic-modifying gene mutations at diagnosis (IDH1/2, DNMT3A, TET2) (Shih et al 2002, Wakita et al 2013). Depending on the management choice at the initial diagnosis and initial CR, the last clinical scenario may be a bridge to a first or second HCT or to a DLI.

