2.2 Secondary Objectives

The secondary objectives of this study are to:

- Define the time to ANC and platelet count recovery
- Define the number of patients proceeding to an alloHCT
- Determine time to progressive disease (PD) or DOR
- Determine event-free survival (EFS)
- Determine OS
- Define the percentage of patients who develop late responses
- Define the number of patients who can receive consolidation and maintenance therapy on this study
- Define the treatment-related mortality rate of this combination
- Determine the percentage of patients who achieve a PR or molecular CR
- Determine the mean elapsed time for patients to achieve molecular CR
- Determine whether quizartinib is tolerable after alloHCT or DLI

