9.7 Event-free Survival (EFS)

Event-free survival is calculated as the number of days from the first date of treatment to the first date of evidence of PD by BM biopsy/aspirate, or death, regardless of cause. Patients who are alive without a disease response assessment of relapsed disease will be censored at the last adequate disease assessment date. Patients without a disease response assessment will be censored at the first date of treatment. This calculation does not pertain to Long Term Follow-up data.

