10.4 Data Analysis

Descriptive statistics, including mean, median, standard deviations, and ranges for all continuous measures, will be tabulated and reported. Percentages and frequencies for all categorical measures will also be presented. Time-to-event endpoints will be reported using Kaplan-Meier estimates, with 95% CIs for median time to event.

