10.4.2 Efficacy Analysis

All efficacy analyses will be performed using the Efficacy Analysis Set.

The ORR is defined as the proportion of patients achieving a response of CR or CRi at the time of the recovery assessment. For ORR, point estimates and the associated 95% CIs (based on the Clopper-Pearson method) will be calculated.

For DOR, the estimate of the median based on Kaplan-Meier analyses will be reported. For EFS and OS, the estimated rates at 6, 12, and 24 months based on Kaplan-Meier analyses will be reported.

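### Duration of response censors deaths in remission, so its Kaplan-Meier median does not register those deaths and equals or exceeds the time responders stay alive in remission

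*Combined protocol and SAP*

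**What the plan says.** Protocol section 9.5 measures DOR as "the number of days from the time of the first BM biopsy/aspirate where CR or CRi is identified to relapse". Relapse is the only event. Patients still free of relapse are censored at their last disease assessment, and so are patients "who died for reasons other than disease relapse will be censored at the date of the last disease assessment". The section has no rule that censors at transplant, so a death after transplant in remission falls under this rule too.

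Section 10.4.2 adds: "For DOR, the estimate of the median based on Kaplan-Meier analyses will be reported". Section 10.4 says the same in general: "Time-to-event endpoints will be reported using Kaplan-Meier estimates, with 95% CIs for median time to event". Neither section plans a cumulative incidence, another competing-risk estimate or a sensitivity analysis for DOR.

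Event-free survival in section 9.7 treats death differently. It ends at "the first date of evidence of PD by BM biopsy/aspirate, or death, regardless of cause". Its clock starts at first treatment, and it leaves out long-term follow-up data.

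Two passages bear on whether deaths in remission are to be expected. For two of the four patient groups in section 1.5, "the study intervention will likely act as a bridge to either an HCT or a DLI". Section 2.2 lists as a secondary objective: "Define the treatment-related mortality rate of this combination". No rate of death in remission is given anywhere.

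**The concern.** Censoring in a Kaplan-Meier analysis says that the patient stays at the same risk of the event as those still followed. That suits a living patient whose follow-up has stopped. It does not suit a patient who has died in remission, who can never relapse. The resulting curve describes time to relapse in a population in which nobody dies in remission, yet it carries the label duration of response. Most readers take that label to mean how long responders remain alive and in remission.

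At stake is the reading of one secondary result. Two regimens with the same relapse hazard would show about the same DOR even if one of them lost many more responders to infection, hemorrhage or transplant complications. The median cannot tell them apart.

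The censoring date adds a smaller problem. It is the last disease assessment, not the date of death. If disease assessment means the scheduled maintenance marrow (cycles 3, 6, 12 and 24), the widest gap is 12 × 28 = 336 days. Time the patient is known to have lived can therefore be discarded.

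**Working it through.** **The plan's own figure.** The documents give no expected DOR and no calculation for it. The only design calculation is for the response rate: 30 evaluable patients, rejection at 13 or more responses, 27% against 50%, one-sided 0.05. The exact binomial gives a type I error of 0.0395 and power of 0.819, and 30/(1 − 0.10) = 33.3, rounded up to 34. All of this reproduces, and DOR enters none of it.

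**Inputs for DOR.**
- From the documents: relapse is the only event; relapse-free deaths are censored at the last disease assessment; the summary is a Kaplan-Meier median.
- Assumed: constant, independent hazards of relapse and of death in remission; a share q of remissions that end in death, from 10% to 40%; a true median time alive in remission, M.
- M is taken as 26 weeks. The only DOR median in the documents is 13.3 weeks (quizartinib monotherapy, phase I, section 1.2). It serves here as a second illustrative value.

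**Formula.** The total hazard of leaving remission is ln2/M, and the relapse part of it is (1 − q) × ln2/M. Kaplan-Meier with deaths censored estimates the relapse part alone, so its median is M/(1 − q). The relative excess is 1/(1 − q) − 1. The formula takes censoring at the date of death.

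| q (assumed) | Excess | M = 13.3 weeks becomes | M = 26 weeks becomes |
|---|---|---|---|
| 10% | 11% | 14.8 | 28.9 |
| 20% | 25% | 16.6 | 32.5 |
| 30% | 43% | 19.0 | 37.1 |
| 40% | 67% | 22.2 | 43.3 |

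**Simulation at trial size.** Settings: 15 responders (50% of 30), M = 26 weeks, 104 weeks of follow-up, and deaths censored at the last assessment on an assumed 8-week grid. The median over simulated trials under the section 9.5 rule was:

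| q (assumed) | Reported median, weeks | Excess over 26 | Trials with a longer median than when deaths count as events |
|---|---|---|---|
| 10% | 28.2 | 8% | 41% |
| 20% | 31.5 | 21% | 70% |
| 30% | 35.6 | 37% | 84% |
| 40% | 40.9 | 57% | 94% |

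Counting deaths as events gave about 26 weeks throughout. In nearly all the remaining trials the two medians were equal. The section 9.5 rule gave a shorter one in at most 0.2%, a side effect of censoring before the date of death. With q = 0 the two rules agree exactly.

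**Does the reported median rise with toxicity?** Here the relapse median is held at 26 weeks and only the death hazard increases. In large samples the section 9.5 median was 26.0, 25.8, 25.4, 24.8 and 24.3 weeks for q = 0, 10, 20, 30 and 40%. It is nearly flat and falls slightly because of the early censoring date. Time alive in remission shortens to 26 × (1 − 0.40) = 15.6 weeks at q = 40%. The gap opens because the true duration falls while the reported one barely moves.

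**The case against.** The strongest reply is that section 9.5 openly defines a relapse-only endpoint. If deaths are independent of relapse risk, Kaplan-Meier with deaths censored at the date of death estimates the relapse-only median without large-sample bias. The excess is then a difference between two quantities, not an error in estimating one. This stands as a description. It does not remove the point, because the quantity reported exists only in a hypothetical population without deaths in remission, and nothing planned beside it says so.

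Second, deaths are not hidden. Overall survival counts them all, event-free survival counts death ("or death, regardless of cause") within its follow-up limits, and treatment-related mortality is an objective. That also stands, but none of these measures time in remission from first CR or CRi. The different handling of death in sections 9.5 and 9.7 is not itself a contradiction, since two endpoints may have different events.

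Third, the result is imprecise anyway. With 15 responders and a true median of 26 weeks, the simulated medians span about 11 to 50 weeks (95% range). That limits the practical weight, although a systematic shift is not excused by random error.

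A reader might go further and infer three things that the documents do not support:
- That a more toxic regimen yields a longer reported DOR. With the relapse hazard fixed, it does not.
- That deaths in remission will be a material share of first events. No rate is given, and section 1.4 speaks of a possible bridge for some patients only.
- That relapse percentages at fixed times will be misreported. Section 10.4.2 plans only a median for DOR; the 6-, 12- and 24-month rates are for event-free and overall survival.

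**Conclusion.** The point holds in a limited form. As defined, the DOR median is insensitive to deaths in remission. Apart from the rare effect of the early censoring date, it equals or exceeds the time responders stay alive in remission. The direction follows from the text of sections 9.5 and 10.4.2.

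The size does not follow from the text. It rests on an assumed 10% to 40% of remissions ending in death and on constant, independent hazards. Under these the excess is 11% to 67% by formula, and about 8% to 57% at trial size with a true median of 26 weeks. If no responder dies in remission before the median, there is no excess.

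The consequence is confined to a secondary, descriptive endpoint without a test or threshold. It would be wrong to infer that the primary conclusion is at risk: the rule of 13 responses in 30, its error rates and the 34 patients enrolled are untouched. The change is still worth making before analysis, because it alters a reported result and costs little.

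**What to change.** In section 9.5, define DOR as the time from the first marrow showing CR or CRi to relapse or death from any cause, whichever comes first. Censor only living, relapse-free patients, at their last disease assessment. An all-cause rule also removes the need to decide whether a death was due to relapse.

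In section 10.4.2, report the Kaplan-Meier median of that endpoint, together with the cumulative incidence of relapse with death in remission as a competing event. The present relapse-only rule may stay as a sensitivity analysis, labelled as such.

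The cost is one sentence in each section. No patient or visit is added, because disease response and survival status are already collected every 6 months for 2 years after treatment (section 6.4.6). The price to the sponsor is a somewhat shorter reported median if responders die in remission.

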9.6 Time-to-Progression (TTP)

Time-to-progression is defined as the number of days between diagnosis of relapse or refractory AML to disease progression, confirmed by bone marrow biopsy.

9.7 Event-free Survival (EFS)

Event-free survival is calculated as the number of days from the first date of treatment to the first date of evidence of PD by BM biopsy/aspirate, or death, regardless of cause. Patients who are alive without a disease response assessment of relapsed disease will be censored at the last adequate disease assessment date. Patients without a disease response assessment will be censored at the first date of treatment. This calculation does not pertain to Long Term Follow-up data.

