6.4.5 End of Treatment/Early Termination Visit

Patients will complete the study at the time of PD, if they withdraw consent, if they withdraw due to an AE, or at the time the study is terminated. If either study treatment or patients are discontinued, the reason will be recorded in the eCRF and source document. Patients who are removed from treatment for reasons other than death or disease progression (PD) are considered to be patients who have terminated early. Reasons for discontinuation include one of the following: AEs, protocol violation, patient withdraws consent, patient is lost to follow-up, administrative reasons (including study closure), death, or other. Patients who complete or discontinue from the study should have the following study completion/early withdrawal evaluations performed as soon as possible after the day of study completion/early withdrawal.

- Physical examination and vital signs

CONFIDENTIAL

STUDY DRUG: QUIZARTINIB
 PROTOCOL DATE: 10 AUGUST 2020

DEVELOPMENT INNOVATIONS STUDY NUMBER: AML 48
 VERSION 4.0

- ECOG performance status
- AE monitoring
- Concomitant medication review
- CBC and clinical chemistry panels
- BM biopsy and aspirate with FLT3 mutation testing, if applicable
- ECG and QTcF assessment, if applicable

Patients prematurely discontinuing from the study must be followed for AE and concomitant medication use for 30 days following the last administration of study drugs or until resolution/stabilization of an ongoing AE attributed to the medication.

Patients who discontinue from the study may be treated with other therapies at the discretion of the Investigator.

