9.8 Recurrence of Disease

Recurrent malignancy will be defined by hematologic criteria. Recurrent malignancy will also be defined as any unplanned medical intervention designed to prevent progression of malignant disease in patients who have molecular, cytogenetic, or flow cytometric evidence of malignant cells after transplantation.

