AML and ALL (con“t)	Intermediate risk: CR2, CR3+	Complete remission 2nd or greater (CR2/+)[†]: Recipient achieved CR as defined above, relapsed and achieved CR again. Final pre-HSCT status must be CR.
AML and ALL (con“t)	High risk (not in remission):	Never treated: The recipient was diagnosed with acute leukemia and never treated. For example, this disease status may be appropriate if MDS was initially diagnosed and

CONFIDENTIAL

ASBMT Diagnosis Category	ASBMT RFI Classification	CIBMTR Classification [^]
	Never treated Primary Induction Failure (PIF) Relapse	
treated, the MDS then transformed into AML, and a decision was made to proceed immediately to transplant instead of treating the AML with therapy.
 
Primary Induction Failure (PIF): The recipient was treated for acute leukemia but never achieved durable* complete remission with any therapy (*including relapsed < 1 mo from CR1 determination). The term “PIF” is not limited to the number of treatments used unsuccessfully.
 
Relapse: Recurrence of disease after CR. Relapse is defined as:
 
 • $\geq 5\%$ blasts in the marrow • Extramedullary disease • Reappearance of cytogenetic abnormalities and/or molecular markers associated with the diagnosis that, in the judgement of a physician, are at a level representing relapse. • Although CIBMTR collects information upon the number of the relapse, this information is not needed for the ASBMT RFI

Source: https://higherlogicdownload.s3.amazonaws.com/ASBMT/43a1f41f-55cb-4c97-9e78-c03e867db505/UploadedImages/ASBMT_RFI_2018B_CIBMTR_Disease_Classifications.pdf

CONFIDENTIAL

STUDY DRUG: QUIZARTINIB
 PROTOCOL DATE: 10 AUGUST 2020

DEVELOPMENT INNOVATIONS STUDY NUMBER: AML 48
 VERSION 4.0

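### The EFS censoring rules in Section 9.7 do not match its event definition, and TTP in Section 9.6 starts before treatment

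*Combined protocol and SAP*

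**What the plan says.** - **Event.** Section 9.7 measures EFS from first treatment to "the first date of evidence of PD by BM biopsy/aspirate, or death, regardless of cause".
- **Censoring of living patients.** "Patients who are alive without a disease response assessment of relapsed disease will be censored at the last adequate disease assessment date".
- **Censoring of unassessed patients.** "Patients without a disease response assessment will be censored at the first date of treatment". Section 9.7 then ends by keeping long-term follow-up data out of the calculation.
- **Relapse, recurrence, failure.** Appendix E defines relapse as "Recurrence of disease after CR". Section 9.8 states "Recurrent malignancy will be defined by hematologic criteria" without listing those criteria. Section 9.4 states "Treatment failure is defined as patients who have achieved less than a PR at the time of response assessment", but Section 9.7 does not name treatment failure as an event.
- **Leaving the study.** Section 6.4.5 says "Patients will complete the study at the time of PD" and gives the reasons for discontinuation as "one of the following: AEs, protocol violation, patient withdraws consent, patient is lost to follow-up, administrative reasons (including study closure), death, or other".
- **TTP.** Section 9.6 counts days from the diagnosis of relapsed or refractory AML to progression confirmed on marrow. EFS and OS (Section 9.9) count from first treatment.
- **Use.** Section 2.3.2 lists EFS, and time to PD or DOR, as secondary endpoints. Section 10.4.2 reports Kaplan-Meier EFS at 6, 12 and 24 months.

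**The concern.** The event turns on PD, but the censoring of living patients turns on relapse. A patient who never reaches CR cannot relapse in the sense of Appendix E. Such a patient with PD on marrow therefore meets both the event rule and the censoring rule. Marrow is named as the means of showing PD, but no threshold or reference marrow is given for disease that never cleared.

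The day-0 rule omits the condition that the patient be alive, although the sentence before it includes one. A patient who dies before the first marrow is an event under the first sentence and contributes no time under the third.

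A living never-responder with no recorded PD is censored at the last marrow. That censoring is probably informative, because it removes patients for whom treatment has not worked, and what happens to them in long-term follow-up is kept out of EFS. Kaplan-Meier estimates assume that censoring is uninformative.

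TTP begins at a diagnosis that is itself an entry criterion, so it includes pre-treatment time in which no on-study event can occur.

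At stake is whether two analysts following Sections 9.6 and 9.7 would report the same secondary results from the same data.

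**Working it through.** **1. The plan's own figures.** None is stated for EFS or TTP. The ORR design reproduces: with n = 30 and a cut-off of 13, P(X ≥ 13 | 0.27) = 0.0395 and P(X ≥ 13 | 0.50) = 0.819; 30/0.9 = 33.3, rounded up to 34. None of these uses EFS or TTP.

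**2. The three sentences of Section 9.7 applied literally.**

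| Patient | Sentence 1 | Sentence 2 | Sentence 3 |
|---|---|---|---|
| Alive, CR then marrow relapse | event (taking relapse as PD) | not censored | does not apply |
| Alive, never CR, marrow called PD | event | censored | does not apply |
| Alive, never CR, no PD recorded | no event | censored at last marrow | does not apply |
| Died before the Day 21 marrow | event | does not apply | censored at day 0 |

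Rows 2 and 4 contradict themselves. Row 3 is the probably informative censoring.

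**3. Size for never-responders.** From the documents: ORR 50% (target) or 27% (null), and the recovery marrow at Day 35. Assumed: responders' median EFS m = 6 months from Day 35, no early deaths, and a share c of never-responders with a recorded event (PD or on-study death) at Day 35, the rest censored then. With d = 35/30.4375 = 1.15 months,

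EFS(t) = [1 − (1 − ORR)·c] × 2^(−(t − d)/m).

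At 6 months the second factor is 2^(−4.85/6) = 0.571.

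| Case | c = 0 | c = 0.5 | c = 1 |
|---|---|---|---|
| ORR 50%, 6 months | 0.571 | 0.75 × 0.571 = 0.428 | 0.5 × 0.571 = 0.286 |
| ORR 27%, 6 months | 0.571 | 0.635 × 0.571 = 0.363 | 0.27 × 0.571 = 0.154 |
| ORR 50%, 12 months | 0.286 | 0.214 | 0.143 |
| ORR 50%, m = 12, 6 months | 0.756 | 0.567 | 0.378 |

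Counting failure to reach CR or CRi as an event gives the c = 1 column, so the two definitions agree when every never-responder has a recorded event.

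**4. Size for early deaths.** Assume 10% (about 3 of 34) die before any marrow, with 50% responders overall and m = 6. At 6 months:

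- c = 0: 0.9 × 0.571 = 0.514 with deaths as events; 0.571 with day-0 censoring.
- c = 1: 0.5 × 0.571 = 0.286 with deaths as events; (0.5/0.9) × 0.571 = 0.317 with day-0 censoring.

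**5. A second illustration with counts.** Assume 30 patients: 15 responders (3 relapsing by 6 months), 12 living non-responders last assessed on Day 35, and 3 deaths on Day 14 without a marrow. Six-month EFS:

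- Non-responders and deaths both events: 12/30 = 40.0%.
- Non-responders events, deaths censored at day 0: 12/27 = 44.4%.
- Non-responders censored, deaths events: (27/30) × (12/15) = 72.0%.
- Both censored: 12/15 = 80.0%.

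**6. TTP.** Each day between diagnosis and first dose adds one day. If the screening marrow (Section 6.2, within 7 days before treatment) is the qualifying diagnosis, the shift is at most 7/30.4375 = 0.23 months. The documents set no limit on an earlier diagnosis.

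**The case against.** The best defence is that the first sentence of Section 9.7 defines events and the later ones deal only with patients who have none. Section 9.7 does not cite Appendix E, which is called on at baseline and in long-term follow-up. On that reading marrow PD and early death are both events, and *relapsed* is loose wording for PD. This is probably the intent, but the text states no order of precedence and the PD criterion is missing either way. Section 10.3 mentions patients who die before their first assessment, but it joins that condition with *and*, so their place in the Efficacy Analysis Set is itself unclear.

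A reader might infer more than the documents support:

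- *That no AML method for progression is named, because Section 11.3.1 mentions RECIST.* Sections 9.6 and 9.7 name marrow. Section 11.3.1 concerns SAE reporting and gives RECIST as a solid-tumour example. Only the criterion is missing.
- *That Section 6.4.5 forces sites to record a non-responder as PD or as other.* Section 3.3 also allows discontinuation for conditions needing treatment that the protocol does not permit, and the eCRF is not among the documents.
- *That non-responders are lost once they start new therapy.* Section 5 does say they are followed until then, but it also assesses outcomes for all patients for 24 months after last treatment. Those data can support OS; Section 9.7 keeps long-term follow-up data out of EFS.
- *That non-response must be an EFS event.* That changes the estimand. Section 5.2 lets PR patients proceed to re-induction or to HCT/CT, and late responses are an objective in Section 2.2.

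It is also fair that the sizes rest on assumed inputs, and that the early-death effect of about 3 to 6 points is small beside sampling error: 1.96 × √(0.29 × 0.71/34) is about 15 points.

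**Conclusion.** The mismatch stands on the text. Two kinds of patient are both event and censored under Section 9.7, PD has no criterion for patients who never reach CR, and TTP has a different origin from EFS and OS.

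The size for this trial is unknown. Six-month EFS of 29% to 57% illustrates what turns on how many never-responders have a recorded event, given ORR 50%, a 6-month responder median and no early deaths. The difference from counting non-response as an event is zero if all have one. The 40% to 80% range comes from different assumptions; neither range estimates this trial's result.

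A reader might infer that EFS would not distinguish the null response rate from the target. That needs c = 0, with no never-responder having recorded PD or dying on study, and the documents do not establish this. At c = 1 the two rates give 15% and 29%.

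Nor is the direction of bias settled against an EFS that used follow-up deaths. At ORR 50%, c = 0 and m = 6, assumed never-responder median survival of 3, 6 or 9 months from Day 35 gives 45%, 57% or 63%, against 57% as written.

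TTP matters less: Section 2.3.2 pairs time to PD with DOR, and Section 10.4.2 names no TTP estimate. Both endpoints are secondary and descriptive, and the ORR test, alpha, power and sample size are untouched. This should be corrected before analysis, but it does not threaten the primary conclusion.

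**What to change.** - **(a)** In the second sentence of Section 9.7, make the condition for censoring *alive without PD or relapse*, so that it mirrors the event. State the marrow criterion and the reference marrow for PD in patients who never reach CR.
- **(b)** Limit the third sentence to patients who are *alive* and unassessed, so that deaths before the first marrow are events.
- **(c)** Start TTP in Section 9.6 at the first date of treatment.
- **(d)** Add a sensitivity EFS analysis that counts failure to reach CR or CRi by the last induction recovery marrow (Cycle 1 Day 35, or Cycle 2 Day 35 after re-induction) as an event. Specify the event date, a rule for patients with no recovery marrow, and a rule for PR patients going to HCT/CT and for late responders.

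The cost is protocol and SAP wording plus one extra analysis. The induction marrows and on-study deaths are already collected. EFS and TTP may look slightly less favourable.
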